## **Primary efficacy analysis**

The primary efficacy endpoint will be reported using descriptive statistics only. The analgesic effect will be assessed as the proportion of participants that has a reduction of pain intensity to a score of 4 or below at 15 min and within 30 minutes post IMP (relative to baseline). A 95% confidence interval for the proportion of the participants with a pain reduction of 4 or less within the first 30mins post IMP will be evaluated and reported for each age group and for all subjects.

The pain intensity score is measured using different scales for each of the three age groups:

- Numerical Rating Scale, a self-reported ordinal, categorical scale with values 0-10, interval 1 for subjects aged 9 and less than 18.
- Wong-Baker, a self-reported ordinal, categorical scale with values 0-10, interval 2 for subjects aged 5 and less than 9.
- FLACC, an ordinal, categorical scale with values 0-10, interval 1 for subjects aged 1 and less than 5. Pain intensity assessment for this age group to be conducted by the investigator.

Given that the pain intensity is measured using different scales for each of the three age groups, subgroup analyses stratified by measurement scale may be appropriate. Graphical representation of pain intensity scores measured within 30mins post IMP administration will be produced in the form of boxplots for each age category/assessment scale.

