Statistical Methods	
General principles The primary objective of this study is to investigate the safety, tolerability and analgesic effects of CT001 in pediatric participants when used in an acute care setting.
 
Data will be summarised using descriptive statistics. For continuous endpoints, the descriptive statistics include number of subjects, mean, median, standard deviation, standard error, lower and upper quartiles, minimum, and maximum. For categorical endpoints, frequency, and percentage will be given. Figures showing population distributions, such as box plots and histograms, will be reported for all applicable endpoints. The method of handling missing data for efficacy endpoints will be described for each set of endpoints. Missing data will not be imputed for safety endpoints.
 
Sample size estimation So far, data from 375 children on IN sufentanil/ketamine show a safe and tolerable combination (data from PDC 01-0201, PDC 01-0203 and PDC 01-0206). Thus, from a safety perspective it is expected that 150 patients will be sufficient to capture and confirm the adverse event profile of the IMP.
 
A formal sample size calculation was made for the primary efficacy endpoint on the basis of expecting a responder rate of 60%. A previous study reported a responder rate of 71.6 %, defined as pain intensity <math>\leq 3</math> at 30 min post IMP (16). With a sample of 113 patients, a one-sample one-sided proportion design would provide at least 80% power to show that the responder rate is more than to 60%, with a significance level of 5%. Accounting for an approximate 25% dropout rate the resulting sample size is 150.
 
Study populations The full analysis set (FAS) will consist of all patients who received at least one dose of study treatment (CT001). The FAS follows the intention-to-treat (ITT) principle, i.e. patients will be analysed regardless of whether treatment was received as planned. The FAS will be used for all analyses of primary and secondary safety and efficacy objectives.
 
The FAS will be used to tabulate demographic data, baseline disease characteristics, and subject disposition.
 
Statistical analysis of the primary endpoints The primary objective of the study will be evaluated using the FAS population. Data will further be evaluated by age group.
 
Descriptive statistics will be used for safety variables. Safety variables of special interest consist of vital signs, respiratory rate, pulse rate, oxygen saturation (SpO2), heart rate as well as sedation.
 
Clinically significant out-of-range values and clinically significant relevant changes of values will be described descriptive statistics, number of subjects, number of events.
 
Adverse events will be coded according to the MedDRA dictionary. The frequencies of adverse events will be tabulated by body system and "preferred term".

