----------------------------	---

	
The analgesic efficacy variable, responder rate (pain intensity of 4 or below at 15 min and within 30 min post IMP), will be reported using descriptive statistics.
 
Statistical analysis of secondary endpoints
 
All secondary endpoints will be analysed using descriptive statistics. Besides reporting summary descriptive statistics, Means and corresponding 90% symmetric confidence intervals estimated using the change from baseline in the respective variable unit.

--	--

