### 7.1 Estimation of Sample Size

So far, data from 375 children on IN sufentanil/ketamine show a safe and tolerable combination (data from PDC 01-0201, PDC 01-0203 and PDC 01-0206). Thus, from a safety perspective it is expected that 150 patients will be sufficient to capture and confirm the adverse event profile of the IMP. Furthermore, a sample size calculation was made for the primary efficacy endpoint on the basis of expecting a responder rate of 60%. A previous study reported a responder rate of 71.6 %, defined as pain intensity  $\leq 3$  at 30 min post IMP (16). With a sample of 113 patients, a one-sample one-sided proportion design would provide at least 80% power to show that the responder rate is more than to 60%, with a significance level of 5%. Accounting for an approximate 25% dropout rate the resulting sample size is 150.

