### 7.4 Method of statistical analyses

All data will be presented as descriptive analyses only. Continuous variables will be summarised using descriptive statistics (number of participants, mean, standard deviation [SD], minimum, median, maximum) by age group and as total. Categorical variables will be summarised in frequency tables (frequency and proportion) by age group and as total. Graphical presentations will be used as appropriate. All changes from baseline endpoints are calculated as the value of the corresponding timepoint minus the value at baseline.

Variables that are based on ordinal scales, such as pain intensity, will be summarized using median and interquartile range.

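### The efficacy basis for the sample size is the power of a one-sided test against 60%, but the plan contains no such test and never compares any result with 60%.

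*Combined protocol and SAP*

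**What the plan says.** **Sample size (section 7.1, repeated in the synopsis).** Two bases are given for 150.

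- Safety: data from 375 children in three earlier studies are taken to show that 150 will be enough to confirm the adverse event profile.
- Efficacy: the synopsis says "A formal sample size calculation was made for the primary efficacy endpoint on the basis of expecting a responder rate of 60" per cent. With 113 patients, "a one-sample one-sided proportion design would provide at least 80% power to show that the responder rate is more than to 60" per cent, at a 5% significance level. On the source, "A previous study reported a responder rate of 71.6 %, defined as pain intensity" of 3 or less at 30 min. Then: "Accounting for an approximate 25% dropout rate the resulting sample size is 150".

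**Analysis.** Section 7.4 opens with "All data will be presented as descriptive analyses only". For primary efficacy, section 7.4.1 says "The primary efficacy endpoint will be reported using descriptive statistics only", and the synopsis agrees: "responder rate (pain intensity of 4 or below at 15 min and within 30 min post IMP), will be reported using descriptive statistics". The one interval planned for primary efficacy, by age group and overall, is "A 95% confidence interval for the proportion of the participants with a pain reduction of 4 or less within the first 30mins post IMP". It has no reference value and no named method.

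**Endpoints and numbers.** Section 6.1.1 has two primary responder rates, both for a score of 4 or below: at 15 min, and at any time within 30 min. The synopsis and sections 4.1 and 4.5 plan for 150 evaluable participants. Section 7 leaves technical detail to a separate SAP, to be approved before database lock.

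**The concern.** Power is a property of a decision rule, and this plan has none for efficacy. A reader of section 7.1 will take the trial as sized to show a rate above 60%, yet no planned output makes or tests that claim.

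The inputs are also unclear. Section 7.1 calls 60% the expected rate, although it is the value to be exceeded. It cites 71.6% without stating it as the assumed true rate. It speaks of one primary efficacy endpoint where section 6.1.1 has two.

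The trial is open-label and single-arm, so results are visible as they accrue. With 60% in the text but no fixed endpoint, level or rule, a claim to have exceeded it could later be attached to whichever endpoint or interval level happens to pass.

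Two smaller defects lie in the same paragraph of section 7.4.1. Read literally, the interval is for a reduction of 4 points or less, which is a different quantity from a score of 4 or below. And the 15-min primary endpoint has no interval.

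**Working it through.** **Inputs.** From section 7.1: null rate p0 = 0.60, one-sided level 5%, power 80%, n = 113, dropout about 25%, N = 150. The true rate p1 = 0.716 is inferred: it is the only other rate given there.

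**1. Reproducing 113.** Normal approximation:

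n = [(z0.95·√(p0·q0) + z0.80·√(p1·q1)) / (p1 − p0)]²

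= [(0.8058 + 0.3795) / 0.116]² = 104.4

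Continuity correction: n/4 · [1 + √(1 + 2/(n·0.116))]² = 112.9, that is **113**. With the same method, p1 = 71.5% gives 115 and 71.7% gives 111. So 71.6% is evidently the alternative used, and 60% is the null.

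Dropout: 113/0.75 = 150.7, against 150 stated (150 × 0.75 = 112.5). The difference is immaterial.

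**2. The test that was powered (exact binomial, one-sided 5%, against 60%).**

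| n | responders needed | actual level | power at 71.6% | power at 70% |
|---|---|---|---|---|
| 113 | 77 | 4.6% | 82.2% | 70.7% |
| 150 | 101 | 3.9% | 89.3% | 79.0% |

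If the true rate were the 60% that section 7.1 calls expected, the test would succeed with probability equal to its level: 4.6% at 113.

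**3. The planned 95% interval, if it were read against 60%.** The method is assumed to be Clopper-Pearson. Requiring the lower limit to exceed 60% is a one-sided 2.5% rule, stricter than the 5% used for sizing.

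| n | responders needed | power at 71.6% | power at 70% |
|---|---|---|---|
| 113 | 79 | 69.6% | 55.4% |
| 150 | 103 | 81.3% | 67.5% |

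With a Wilson interval at 150, 102 are needed, and power is 85.7% at 71.6% and 73.6% at 70%.

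**4. Where the two readings disagree at 150.** With 101 responders the 90% Clopper-Pearson lower limit is 60.5% and the 95% lower limit is 59.2%. With 102 they are 61.2% and 59.9%. In both cases the one-sided 5% test passes and the 95% interval does not clear 60%.

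**5. Precision, which a descriptive plan can deliver.** 95% Clopper-Pearson at an observed 70%:

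| responders/n | interval | half-width (points) |
|---|---|---|
| 105/150 | 62.0 to 77.2 | 7.6 |
| 79/113 | 60.6 to 78.2 | 8.8 |
| 28/40 | 53.5 to 83.4 | 15.0 |
| 14/20 | 45.7 to 88.1 | 21.2 |

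The values 40 and 20 are the age-group minimums in section 5.4.

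**The case against.** The strongest reply is that little depends on the mismatch.

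- **Safety basis.** Section 7.1 gives it first, and safety is the first-listed primary objective. Without the power sentence, 150 would still have a stated rationale. This stands: the fault is confined to the efficacy basis.
- **The interval can serve as the test.** Anyone can compare the within-30-min interval with 60%, and at 150 evaluable that keeps 81.3% power. This stands in part. The plan does not state the comparison, its level is not the one used for sizing, and the 81.3% depends on a true rate of 71.6%.
- **The SAP will settle it.** It can correct the interval wording and add the 15-min interval. It cannot add the powered test without contradicting the protocol's restriction to descriptive statistics.
- **The endpoint is evident.** The source figure is for 30 min and the only interval is for within 30 min, which does suggest that endpoint. Section 7.1 still does not say so.

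A reader might go further and infer that the trial is too small or 150 unjustified. The documents do not support that: the arithmetic reproduces, and the target is 150 evaluable. Nor does borrowing 71.6% from another definition make it optimistic in itself. A score of 3 or less at 30 min is stricter than 4 or below at any time within 30 min, so for that endpoint the difference in definition alone is conservative; for 15 min the direction is unknown. Finally, the interval wording need not mean that a different endpoint is intended: the sentence before it, the synopsis and section 6.1.1 all use a score of 4 or below, so it looks like a drafting slip.

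**Conclusion.** The point holds for the efficacy basis only. Section 7.1 and the synopsis claim at least 80% power for a one-sided 5% test against 60%, and sections 7.4 and 7.4.1 and the synopsis plan description without any such test or comparison. This should be fixed, but it does not threaten the trial: no change to the number of participants follows from it.

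The size of the effect depends on the number evaluable and on the true rate. Reading the 95% interval against 60% gives 81.3% power only at 150 evaluable and a true 71.6%; it falls to 69.6% at 113, or to 67.5% at 150 if the true rate is 70%. These figures assume a Clopper-Pearson interval and, for 71.6%, that the cited rate is the intended alternative. The interval wording and the missing 15-min interval are lesser points and do not add to the weight.

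**What to change.** Choose one option by protocol amendment. Either should be settled before outcome data are reviewed: in an open-label trial, dropping the 60% benchmark after seeing results is as open to question as adding a test.

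**(a) Preferred, because it keeps the descriptive plan.** Retain the safety rationale. Delete the power claim and the 60% and 71.6% inputs from section 7.1 and the synopsis. Justify the number by the expected 95% Clopper-Pearson half-width at a rate of 70%: about 7.6 points at 150, 8.8 at 113, 15.0 at 40 and 21.2 at 20.

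**(b) Keep the power claim.** State a null rate of 60% and an assumed true rate of 71.6%, noting that the source used a score of 3 or less at 30 min. Name which responder rate the calculation serves. Add an exact one-sided 5% binomial test for it and lift the descriptive-only restriction for that endpoint. Say that the test (equivalently, the 90% Clopper-Pearson lower limit) decides and that the 95% interval is descriptive, since the two disagree at 101 and 102 of 150.

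**Under either option,** reword the interval in section 7.4.1 as the proportion of participants with a pain score of 4 or below, name its method, and report it at 15 min and within 30 min.

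Cost: text only, with no change to numbers, visits or data collection. Both options change protocol text, so section 8.1 applies. Option (b) adds a confirmatory analysis and may be judged a substantial amendment.

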### **7.4.2 Analyses addressing the secondary objectives**

#### **Secondary safety and tolerability analysis**

#### **Treatment Satisfaction**

The general treatment satisfaction score is an ordinal, categorical variable which will be reported as median and IQR by age group and for all subjects.

### Feasibility (Acceptance of Nasal administration)

The categorical responses 'Yes', 'No' and 'I don't know' by the child or their caregiver to the question: '*If you were in this situation again and needed pain medication, would you like to receive the nasal spray (relative to an injection, tablet or suppository for the pain)?*' will be summarised counts and percentages by age group and for all subjects. Frequency graphs may also be used to summarise the data.

### Medication Errors

Counts and percentages by age group and dose level will be used to summarise deviations in the administration of the IMP that result in higher or lower dosage than planned.

### Secondary efficacy analysis

#### Need for Supplemental Medication

The number of children receiving additional analgesics will be summarized using counts, frequency tables and graphs by type, dose, and timepoint.

#### Maximum change in pain intensity within 30 min post IMP administration

Maximum change in pain intensity within 30 min post IMP administration (relative to baseline) will be computed for each subject. The maximum change will be summarised by the median and IQR by age group and dose level. Average time from IMP to maximum change in pain intensity will also be reported.

#### 30% (or more) reduction in pain intensity within 30 min post IMP administration

The number of subjects that achieve at least 30% reduction in pain intensity relative to baseline within 30 min post IMP administration will be summarized using counts and percentages (frequency tables) and reported by type, dose level, and timepoint.

#### Change in pain intensity

The change in pain intensity from baseline will be computed for each subject at 10, 15, 20, 30, 45 and 60 min post IMP and this parameter will be summarized by the median and IQR and reported by age group and dose level.

## 7.5 Data Collection / Case Report Forms

Data will be collected using an electronic data capture (EDC) solution. Electronic Case report forms (eCRFs) will be utilised for recording data from each subject meeting the eligibility criteria and being

included in the study. The eCRF system, Viedoc™, will be available on an internet portal accessible through any standard computer device with internet access. All study staff responsible for entering data into the eCRF system will be trained at the Investigator meeting and/or by the Clinical Research Associate (CRA) prior to the start-up of the study. A personal log-in will be provided for all responsible personnel to allow for an audit trail relating to the study data to be maintained. No clinical trial information will be transferred via the eCRF system until the site has been qualified through completion of a validation eCRF.

All evaluations performed shall be entered in a timely manner into the eCRF by a member of the site staff delegated responsibility for this specific task by the Principal Investigator (PI) of the clinical site. It is the responsibility of the Investigator to ensure that the eCRFs are properly completed. The data in the eCRFs should be consistent with the relevant source documents. The Investigator will sign the designated signature fields of the eCRF data entry screens to confirm that the information on each screen is accurate and complete. All data must be stored in an unidentifiable form treated with strict confidentiality in accordance with applicable data protection regulations.

Captured data will be monitored electronically and Source Data Verification (SDV) will take place at the site, i.e. relevant information (as outlined in the monitoring plan) will be verified against the individual subject records unless the eCRF is considered source data.

Any inconsistencies will be presented as queries; either as automatically generated queries if raised by the logical data checks of the eCRF system, or by manually generated queries if raised by the data validation checks or the SDV performed by the Data Manager (DM) or the CRA respectively. Queries shall be resolved in a timely manner by a trained member of the site staff.

## 7.6 Data Management

Data will be transmitted electronically into the web-based EDC system. Upon receipt, data will be coded according to pre-specified dictionaries and in accordance with the CROs Standard Operating Procedures (SOP). The handling of data, including data quality control, will comply with all applicable regulatory guidelines.

# 8 REGULATORY AND ADMINISTRATIVE PROCEDURES

## 8.1 Institutional Review

The procedures set out in this study protocol are designed to ensure that the Sponsor, the CRO and Investigator abide by the principles of the Guideline for Good Clinical Practice (GCP) of the International Conference of Harmonization (ICH) Good Clinical Practice as last amended in 2016, in the conduct, evaluation and documentation of this study (17). Further, the study will be conducted

in accordance with the moral, ethical and scientific principles governing clinical research as set out in the World Medical Association. WMA Declaration of Helsinki – Ethical Principles for Medical Research Involving Human Subjects. World Medical Association 1964, Amended 2013. The study will further be carried out in accordance with any additional local legal requirements.

The Protocol and the Subject Information Sheet / Informed Consent Form / Assent Form will be approved by the relevant Competent Authorities and Ethics Committees, and possibly other public bodies according to local requirements before commencement. If a protocol amendment is necessary, this will be prepared with the agreement of the Principal Investigator and signed by the relevant parties. If the amendment is considered substantial, it will be submitted to the Competent Authorities and Ethics Committees, and possibly other public bodies according to local requirements for review and approval. The protocol amendment will not be implemented before the required approvals are obtained. Minor amendments which do not affect the safety or physical or mental integrity of the clinical trial subjects or the scientific value of the trial (i.e. non-substantial amendments) will not be submitted to Competent Authorities or Ethics Committees.

SUSAR reports and Periodic Safety Reports will be sent to Competent Authorities and Ethics Committees according to local regulations.

## 8.2 Subject Information / Informed Consent

In the following, the word study subject includes the participant and/or the accompanying parent/legal guardian.

The Investigator is responsible for giving the study subject full and adequate verbal and written information about the nature, purpose, possible risk, and benefit of the study. Information about the study and obtaining consent may be delegated to an experienced study nurse. Study subjects must also be notified that they are free to withdraw from the study at any time. The subjects should have reasonable time to read and understand the information before signing. The Investigator is responsible for obtaining signed informed consent from all subjects before including the subject in any study related procedures. A copy of the participant information and of the signed Informed Consent Form / Assent Form in local language, will be given to the subjects. One original copy of the signed Informed Consent form / Assent Form will be kept by the subject and one copy will be retained at the study site.

## 8.3 Subject Confidentiality and Data Protection

### 8.3.1 Subject confidentiality

The Investigator must ensure that subject's confidentiality will be maintained. eCRFs or other documents submitted to the sponsor should only identify subjects by their initials and study number. The Investigator should keep a separate log of subject codes and names. Documents not for submission to the Sponsor, e.g., subject's completed Consent Forms, should be retained by the Investigator in strict confidence.

The Investigator is required to record primary efficacy and safety data, concomitant medication, and subject progress in the subject's file/notes/medical record.

The subject's medical records (source data) will be reviewed by the study monitor and possibly by other sponsor personnel or regulatory authorities, to verify adequate source documentation, accuracy, and completeness of eCRFs. The review will be conducted with strict adherence to professional standards of confidentiality. No participant identifiable data will be taken out of the investigator site.

All subjects screened for the study will have their initials and birth date entered chronologically on the Subject Screening Log at the initial visit. An explanation for exclusion from admission to the protocol is to be provided on the Subject Screening Log.

